## 1 Revision Control & Approvals

### 1.1 Revision Control

Revision	Date	Update Description	Author/Owner
01	12-DEC-2021	Initial Release	
02	25-MAR-2022	Revisions to Eligibility Criteria	

## 3 Protocol Synopsis

Title:	The effect of acute pudendal nerve stimulation on leak point pressure in women urodynamic early feasibility study
Protocol Number:	CLN-0212
Study Design:	An early feasibility prospective single-arm study
Purpose:	Evaluate the changes in stress introduced Urethral Leak Point Pressures (ULPP) and other urodynamic measurements in response to acute pudendal nerve stimulation (PNS) in patients with a pre-existing implanted urological neurostimulator (Medtronic InterStim™) stimulating the pudendal nerve. Ultimately these data may support the development of subsequent studies of a sensor-controlled neuromodulation treatment for Stress Urinary Incontinence (SUI) and or Mixed urinary Incontinence (MUI).
Objectives:	
Primary Objectives:
 
 
1. Gain initial insights on the effect of acute PNS
 
2. Gain initial insights on the changes in LPP upon acute PNS.
 
 
Secondary Objectives:
 
 
1. Gain initial insights on the effect of acute PNS on the urethral pressure profile (UPP) and other urodynamic measurements.
 

Endpoints:	
Primary Endpoint:
 
 
1. Identification of all study-related adverse events
 
2. Measurement of the changes in ULPP with acute PNS compared to without stimulation.
 
 
Secondary Endpoints:

	
 
1. Measurement of UPP and other urodynamic measurements with and without programmed pudendal nerve stimulation.
 

Study Description:	A urodynamic test (UDT) for eligible subjects with and without acute PNS will be conducted. Prior to introducing the acute PNS, the subject's original stimulation properties will be turned off. The implanted neurostimulator device will be programmed to deliver acute PNS per individual tolerance level with the objective of increasing external urethral sphincter pressure. The ULPP during Valsalva maneuver or forceful coughing will be assessed with and without acute PNS. The ULPP will be assessed at increasing bladder volumes until major detrusor instability, significant leakage (more than drops, stream) or subject discomfort (strong desire to void) is observed. Finally, a UPP with PNS set in an on/off cycling regimen will be conducted to observe the effect on pressures along the length of the urethra.
Visit Schedule:	There are 3 study visits: 1) enrollment (remote visit), 2) acute stimulation/UDT (in person) visit, and 3) a follow up phone call. The second visit is expected to last about 90 minutes
Study Duration:	Approximately 6 months from the first enrollment until completion of data collection.
Study Population:	Female patients with an implantable PNS device.
Number of subjects:	Up to 15 subjects
Inclusion Criteria:	
The subject must meet all the following inclusion criteria:
 
 
1. Women between the ages of 18 and 85 years old, inclusive.
 
2. Implanted with a neurostimulation device for at least 3 months prior to consent (Medtronic InterStim neurostimulator models 3023, 3058, 97810, or similar;)
 
3. Implanted with a tined lead that is placed and functional at the pudendal nerve (Medtronic model 3889 or similar)
 
4. Is capable of understanding clinical study procedures and giving informed consent.
 
5. Willing and able to visit the clinic for the UDT evaluation (study procedure)
 
 
Note: No more than eight subjects having no history of SUI as determined by the investigator.

Exclusion Criteria:	
The subject must not meet any of the following exclusion criteria:
 
 
1. Medically unstable at time of study and unsafe to undergo urodynamic testing as determined by the investigator
 
2. Active bladder cancer
 
3. History of pelvic radiotherapy
 
4. Active gross hematuria
 
5. Active symptomatic urinary tract infection (UTI)
 
6. Active symptomatic uncontrolled bladder instability as determined by the investigator
 

	
 
7. History or symptoms of cystocele, enterocele or rectocele of grade 3 or 4. Per the medical record or as determined by the investigator
 
8. Presence of an artificial urinary sphincter
 
9. Women who are pregnant and/or have given birth in the previous 12 months
 
10. Any medical condition (e.g. Multiple Sclerosis, spinal cord injury, mobility) or uncontrolled chronic disease (e.g. diabetes, renal diseases that requires dialysis) that would interfere with the patient's ability to comply with the protocol and/or may affect the outcome of this study or safety of the subject as determined by the investigator
 
11. BMI>39
 

Data Collection	
Screening data:
 
 
▪ Demographics
 
▪ Medical History
 
▪ Urinary incontinence history
 
▪ Current Medication
 
▪ Eligibility
 
▪ Neurostimulator system (device & electrode) placement and identifiers
 
▪ Prior UDT chart data (optional)
 
 
PNS device settings:
 
 
▪ Device stimulation settings
 
▪ Patient sensations
 
 
PNS procedure data:
 
 
▪ Urodynamic test including ULPP with and without PNS
 
▪ Electromyography test (if separately)
 
▪ Urethral Pressure Profile (optional)
 
▪ Adverse events
 

## 4 Study Rational

### 4.1 Background

Aoki, et al., reported that urinary incontinence symptoms are highly prevalent among women, have a substantial effect on health-related quality of life and are associated with considerable personal and societal expenditure [1]. Two main types are described: stress urinary incontinence (SUI), in which urine leaks in association with physical exertion, and urgency urinary incontinence (UUI), in which urine leaks in association with a sudden compelling desire to void. Women who experience both symptoms are considered as having mixed urinary incontinence (MUI). Overall, SUI is more common (49%) followed by MUI (29%) and pure urge urinary incontinence (21%) [2]. According to Funk, et al., SUI is a highly prevalent condition affecting approximately 13% of women aged 19-44 years and 22% of women aged 45-64 years.[3,4] These women suffer from unpredictable episodes of urinary leakage, which profoundly impairs their quality of life.[5-7] In addition, the economic costs are substantial, totaling over \$20 billion per year in the United States, with 50-75% of these costs due to routine care from incontinence pads, diapers, laundry, dry cleaning, odor control, bed pads and skin care products.[7,8]

Although there are a number of therapies and treatments for SUI, including conservative measures and minimally invasive options, the efficacy of such therapies is limited and supporting data is lacking. There remains a substantially large patient population who have not had success in their treatment or, as with some patients, having undergone implanted meshes and suspension procedures are experiencing significant morbidity. Furthermore, in many individuals, urinary incontinence is complex, involving urge urinary incontinence (UUI), SUI and potentially other related disorders such as Interstitial Cystitis (IC).

Implantable neuromodulation systems have been approved in the US and available to treat the symptoms of UUI and idiopathic urinary retention since the 1990's. These systems provide a beneficial treatment for UUI symptoms by delivering electrical stimulation to the nerves of the sacral spine or pudendal nerve in an open loop manner, without being modulated by any feedback from sensed physiologic conditions. Furthermore, these existing systems are not approved to treat SUI since these systems do not deliver a treatment capable of addressing the mechanism of SUI. Therefore, these existing systems are not capable of treating SUI or MUI, which constitutes a large percentage of the population (78%) with urinary incontinence. Moreover, individuals with UUI alone that are indicated for sacral nerve stimulation (SNS) may eventually develop SUI, resulting in the SNS systems no longer effectively treating all UI symptoms. [5]

This research may help in the development of a novel on-demand neuromodulation therapy for stress and mixed urinary incontinence. This technology may become a valuable treatment for women that have failed more conservative options.

#### 4.2 Study rationale

The primary purpose of this early feasibility prospective study is to gain initial understandings on the effect of acute PNS on the changes in LPP at different bladder volumes. This study is the starting point to gain evidence that the abdominal pressure increases could be detected quickly enough to control the delivery of stimulation to the pudendal nerve resulting in an external sphincter and pelvic floor contraction, thereby preventing an SUI event.

### 5 Objectives and Endpoints

The goal of this study is to collect and analyze subject's urodynamic data, including pressure flow variables with and without PNS during induced elevated abdominal pressure episodes.

Ultimately these data are intended to support the development of subsequent studies of a sensor-controlled neuromodulation treatment for stress and mixed urinary incontinence.

#### 5.1 Primary Objectives

1. Gain initial insights on the effect of acute PNS
2. Gain initial insights on the changes in LPP upon acute PNS

#### 5.2 Primary Endpoints

1. Identification of all study-related adverse events
2. Measurement of the changes in LPP with acute PNS compared to without stimulation

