### 6.1 Number of subjects

Up to 15 subjects

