### 8.1.1 Potential Risks Associated with Urodynamic Test

The risks in this category are related to those of Urodynamic Testing. The estimated probability of these risks occurring is Less Frequent (occurring more than 1% but less than 10% of the time):

- Abrasion to rectum from rectal manometry catheter
- Abrasion to urethra from urethral catheter
- Anxiety
- Discomfort or pain during catheter insertion
- Mild cramping
- Minor bleeding
- Skin irritation (skin electrode adhesive)
- Temporary inability to urinate
- Urinary Tract Infection (UTI)

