### 10 Data Analysis

This early feasibility study is designed to obtain initial insights into evaluating the device design concept with respect to initial clinical safety and device functionality. In general, feasibility studies are not designed or intended to generate statistically valid results. Therefore, 1) there will be no formal statistical hypothesis testing conducted, and 2) sample size is not based on power calculations.

This study is designed to gather information about the pressure waveform parameters during leak point pressure events in urodynamic testing. UDT data will be collected and analyzed to assess the changes and dynamic in LPP, UPP and other UDT parameters with and without acute PNS.

The results of this study may be used to design a statistically powered study to demonstrate safety and efficacy of the new therapy. A sample size of up to 15 will allow initial assessment of safety and improve understanding how LPP changes with acute PNS.

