#### B. Relationship to event

All AEs must have their relationship to study procedure assessed by the clinician who examines and evaluates the participant based on temporal relationship and their clinical judgment. The degree of certainty about causality will be graded using the categories below. In a clinical trial, the study product must always be suspect. However, in this study there is no study product. The study procedure includes standard UDT and a modified PNS. When assessing relationship of the AE to the study procedure the assessing clinician should ask if the UDT and/or the acute PNS caused the AE.

- **Related** – The AE is known to occur with the study procedure, there is a reasonable possibility that the study procedure caused the AE, or there is a temporal relationship between the study procedure and event. Reasonable possibility means that there is clear evidence to suggest a causal relationship between the study procedure and the AE, and other possible contributing factors can be ruled out.
- **Potentially Related** – There is some evidence to suggest a causal relationship or an equally or more likely than not related relationship exists (e.g., the event occurred within a reasonable time after the study procedure). However, other factors may have contributed to the event (e.g., the participant's clinical condition, other concomitant events). Although an AE may rate only as "Potentially Related" upon discovery, the AE can be flagged as requiring more information and later be changed to "Related" or "Not Related", as appropriate.
- **Not Related** – There is not a reasonable possibility that the administration of the study procedure caused the event, there is no temporal relationship between the study procedure and event onset, or an alternate etiology has been established for the event.

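### Primary endpoint 1 pools urodynamic and stimulation adverse events, so the planned tables give no count attributable to acute pudendal nerve stimulation

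*Combined protocol and SAP*

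**What the plan says.** Section 5.1 gives primary objective 1 as "Gain initial insights on the effect of acute PNS". Section 5.2 gives primary endpoint 1 as "Identification of all study-related adverse events". The synopsis describes the design as "An early feasibility prospective single-arm study", and section 6.1 sets the size at "Up to 15 subjects".

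Section 10.2.4 B defines the study procedure as the standard UDT plus a modified PNS. For each AE, "the assessing clinician should ask if the UDT and/or the acute PNS caused the AE". One grade follows for the combined procedure: Related, Potentially Related or Not Related.

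Section 10.2 reports numbers of events, and numbers and percentages of subjects, for serious study-related AEs. It then breaks study-related AEs down by type, severity, seriousness and relationship to the study. Section 10.2.1 collects an event description and the time of onset.

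Section 8.1, by contrast, separates risks by source. Section 8.1.1 lists nine UDT risks: "The estimated probability of these risks occurring is Less Frequent (occurring more than 1% but less than 10% of the time"). Section 8.1.2 lists antibiotic risks. Section 8.1.3 lists three PNS risks during the procedure, at more than 10%.

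Section 10.2.3 puts harm from changes to lead polarity or stimulation current in a sub-category of procedure-related events called Study Equipment.

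**The concern.** The protocol distinguishes the sources of harm when it describes risk and drops the distinction when it plans the analysis. A Related grade is met if an event is known to occur with the procedure or has a temporal relationship to it. A urodynamic harm at the visit is therefore correctly graded Related, and it enters the same count as a stimulation harm.

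Section 10 says the results may be used to design a powered study of the safety and efficacy of the new therapy, and section 4.1 describes that therapy as on-demand neuromodulation. The AE information most useful for that purpose is the part due to stimulation. The protocol also expects PNS harms during the procedure in more than 10% of cases, and no planned table would let a reader check that expectation. If attribution by component and stimulation switching times are not recorded at the visit, the split may not be recoverable afterwards.

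**Working it through.** **No plan figure to reproduce.** The documents give no combined AE rate, event target or power, and section 10 states that "sample size is not based on power calculations".

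**Step 1: does any planned output give a PNS count?**
- Causality grade (10.2.4 B): one grade for UDT and PNS together. The antibiotic is not named in the question at all.
- Tables (10.2): type, severity, seriousness and relationship to the study. None is by component.
- Comparator: a single arm, so no UDT-only rate to subtract.
- Sub-category (10.2.3): captures some stimulation harms, but 10.2 does not say it will be tabulated. Its label is also unclear. The same section uses study equipment to mean the programmer and the urodynamic machine, then excludes both from the category.

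The answer is no.

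**Step 2: how far does event type help?** Comparing the lists in 8.1.1 to 8.1.3:
- On the UDT list only: rectal abrasion, urethral abrasion, anxiety, bleeding, skin irritation, inability to urinate, UTI. That is seven of nine.
- On the UDT and PNS lists: discomfort or pain.
- On the UDT and antibiotic lists: cramping.
- On the PNS list only: dysesthesia.

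Type therefore leaves two of the nine UDT items unattributed. One of them, discomfort or pain, overlaps with PNS. At the edges of its band it is 15 × 0.01 = 0.15 to 15 × 0.10 = 1.5 subjects.

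**Step 3: illustration of the pooled count from UDT alone.** Two assumptions are not in the documents: the band "occurring more than 1% but less than 10% of the time" applies to each of the nine risks, and the risks are independent. Then P(at least one) = 1 − (1 − p)^9.

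| p per risk | P(at least one) | Expected of 15 |
|---|---|---|
| 1% | 8.6% | 1.3 |
| 5% | 37.0% | 5.5 |
| 10% | 61.3% | 9.2 |

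**Step 4: sensitivity to those assumptions** (p = 1% to p = 10%).

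| Assumption | P(at least one) |
|---|---|
| Independent, band per risk | 8.6% to 61.3% |
| Gaussian copula, correlation 0.2 | 8.0% to 51.5% |
| Gaussian copula, correlation 0.5 | 6.2% to 38.6% |
| Gaussian copula, correlation 0.8 | 3.8% to 25.4% |
| No dependence assumption (bounds) | 1% to 90% |
| Band covers the whole list | 1% to 10% (0.15 to 1.5 of 15) |

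The bounds run from p (complete overlap) to 9p (no overlap): 1% to 9% at p = 1%, and 10% to 90% at p = 10%.

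**Step 5: contrast with PNS.** Three PNS risks at their 10% floor, if independent, give 1 − 0.9^3 = 27.1%.

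**The case against.** The strongest reply is that the plan is more informative than a single pooled figure. Related AEs are split by type, the final report covers all AEs, and descriptions and onset times are recorded. With at most 15 subjects a table by type is close to a listing. Table 1 also collects the location and intensity of sensations during stimulation, which is PNS-specific tolerability information. All of this stands, and it narrows the gap. It does not supply a PNS-attributable AE count.

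A reader might infer that the safety result is one undifferentiated rate, that urodynamics alone will put 9% to 61% of subjects in it, or that a high rate could be entirely urodynamic. The documents do not support these readings. The range needs independence and a per-item band, and the harms share catheterisation as a plausible common cause. Section 8.1.3 also puts each PNS harm during the procedure above 10%, higher than any UDT harm. Nor does it follow that the pooled data cannot inform a later study: that study's procedures are not specified, and by-type data remain usable.

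The match of objective 1 to endpoint 1 is inferred from their order. Endpoint 2 does compare stimulation on with off, but on leak point pressure, not on safety.

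Finally, onset phase alone would not isolate PNS. During ON periods the subject is still catheterised, filled and straining, and each period lasts about 60 seconds at most. This objection stands, so phase can only support a clinical attribution.

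**Conclusion.** The point holds as a gap in attribution. Endpoint 1 and the causality grade treat UDT and PNS as one procedure, section 10.2 has no breakdown by component, and the single arm offers no other way to separate them. The planned tables therefore give no PNS-related AE count for objective 1. This conclusion rests on the text alone and does not depend on any figure in the working.

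The practical size is moderate. Type resolves most urodynamic harms. The ambiguous UDT discomfort/pain item is 0.15 to 1.5 of 15 subjects at the protocol's own band, and cramping is ambiguous between UDT and antibiotic. The 9% to 61% figure is an illustration under independence and a per-risk band.

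No hypothesis test or numerical decision threshold is attached to the AE count, so no formal inference is at risk. The change is worth making because it is cheap and is best made before data are collected.

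**What to change.** 1. In 10.2.4 B, grade relatedness separately for UDT, acute PNS and the antibiotic, allowing more than one for an event.
2. In 10.2, tabulate related AEs by component. Report the PNS-related count as the safety result for objective 1, say so in 5.2, and keep the pooled total.
3. Add phase of onset as supporting information: before stimulation, titration, ON period, OFF or filling period, and after the visit. Onset time is already collected. Table 1 lists stimulation settings but no switching times, so on and off times need to be added.
4. State whether the Study Equipment sub-category in 10.2.3 will be tabulated, and clarify what it covers.
5. Reconcile 7.2.2, where amplitude is raised until discomfort is noted, with 10.2.3, where optimisation is not an AE but resulting harm is, and with 8.1.3, which lists temporary discomfort as a risk. The reader must be able to tell how discomfort reached in titration is counted.

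The cost is a few CRF fields, recorded switching times and one further table split, with no change to any study procedure. Attribution remains a clinical judgement, especially for delayed events and for those that begin in an ON period.

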### 5.3 Secondary Objective

1. Gain initial insights on the effect of acute PNS on the urethral pressure profile (UPP) and other urodynamic measurements.

### 5.4 Secondary Endpoint

1. Measure UPP and other urodynamic measurements with and without programmed pudendal nerve stimulation

## 6 Methodology

This study is a feasibility, prospective single arm study. Female subjects with a preexisting operating neurostimulator that is stimulating the pudendal nerve are having a standard urodynamic test (UDT) with and without acute PNS.

### 6.1 Number of subjects

Up to 15 subjects

### 6.2 Study Duration

Approximately 6 months from the first enrollment until completion of data collection.

### 6.3 Study follow-up

There are 3 scheduled visits in this study:

#### 1. Screening and Enrollment Visit

The first visit includes administering informed consent via telephone script and confirming eligibility. Informed Consent (ICF) must be obtained from each eligible patient prior to any study activities. Through the telephone script, potential subjects will consent to receive a copy of the full informed consent form and to provide some information over the phone, listed below:

- Medical history
- Urinary incontinence history
- Neurostimulator information
- Previous UDT and UPP studies (optional)

If a subject doesn't meet study eligibility criteria, he/she should not be consented or enrolled to this study.

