## 7.2 Acute Pudendal Nerve Stimulation (PNS) Setting

- 7.2.1 For the acute stimulation setting, the existing settings may be utilized or other settings within the range approved for use. Gradually increase amplitude and record urethral pressure and

amplitude per investigator.

7.2.2 Continue to increase amplitude progressively until discomfort noted and then reduce incrementally to the last acceptable level to the subject.

7.2.3 Per investigator, the electrode configuration and stimulation parameters may be changed as needed and 7.2.1-7.2.2 repeated.

7.2.4 Turn stimulation off.

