### 7.3 Determine Leak Point Pressure Without and With Stimulation

7.3.1 Move the subject into a sitting or other position as per clinician.

7.3.2 Ensure acute stimulation parameters are set as determined in 7.1.4, above, so that the stimulation pulse train will be delivered continuously when manually turned on. The stimulation will be manually turned off for the infusion delivery periods.

7.3.3 Adjust the urodynamic system to infuse saline at 50 mL, 100mL or increments per investigator at a 50 mL/min infusion rate per physician's discretion.

7.3.4 Start the urodynamic saline infusion into the bladder until the first volume is reached (recommended at either 50mL, 100mL or per investigator) and pause the infusion.

7.3.5 Observe for urinary leakage while patient performs one or more coughs or Valsalva maneuvers with stimulation off to assess LPP.

7.3.6 Turn on stimulation per 7.1.4 and repeat the LPP assessment, using one or more coughs or Valsalva maneuvers as confirmation. Turn off stimulation. Note: This step may be omitted if no leak is observed in 7.3.5 or per physician's discretion.

7.3.7 Continue the urodynamic saline infusion (end the infusion pause mode) and fill the bladder to the next assessment point and stop infusion. Repeat the LPP with stimulation off, and then with stimulation on per 7.3.5 above 7.3.6.

7.3.8 Continue performing Valsalva and forceful coughs at additional bladder volume intervals without and with stimulation (steps) until patient has strong desire to void, bladder reaches major detrusor instability, patient has significant leakage (more than drops), patient has discomfort or any other reason per PI.

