### 9.2 Exclusion Criteria

1. Medically unstable at time of study and unsafe to undergo urodynamic testing as determined by the investigator
2. Active bladder cancer
3. History of pelvic radiotherapy
4. Active gross hematuria
5. Active symptomatic urinary tract infection (UTI)
6. Active symptomatic uncontrolled bladder instability as determined by the investigator
7. History or symptoms of cystocele, enterocele or rectocele of grade 3 or 4. Per the medical record or as determined by the investigator
8. Presence of an artificial urinary sphincter
9. Women who are pregnant and/or have given birth in the previous 12 months
10. Any medical condition (e.g. Multiple Sclerosis, spinal cord injury, mobility) or uncontrolled chronic disease (e.g. diabetes, renal diseases that requires dialysis) that would interfere with the patient's ability to comply with the protocol and/or may affect the outcome of this study or safety of the subject as determined by the investigator

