#### 9.5 Participant Discontinuation/Withdrawal from the Study

Study participants are free to withdraw from participation in the study at any time upon request.

Although Investigators should seek to minimize participant discontinuation or withdrawal from the study except for safety reasons. The PI may discontinue or withdraw a study participant from the study for the following reasons:

- Pregnancy
- Significant study intervention non-compliance
- If any clinical adverse event (AE), or other medical condition or situation occurs such that continued participation in the study would not be in the best interest of the participant
- Disease progression which requires withdraw from participation
- If the participant meets an exclusion criterion (either newly developed or not previously recognized) that precludes further study participation
- The study participant is unable to receive PNS

The reason for participant discontinuation or withdrawal from the study will be recorded on the Study Exit Case Report Form (CRF). Subjects who sign the Informed Consent Form but did not completed the UDT with and without PNS may be replaced.

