### 10.1 General Approach

In this study, only subjects that receive PNS will be included in the analysis. Study subjects that receive acute PNS and complete the UDT will be assessed for safety and evaluation of the changes in LPP and UPP with and without PNS. Study subjects that receive acute PNS and do not complete the UDT will be included in safety analysis only. Study subjects that do not receive acute PNS will be excluded from the study analysis.

Data analysis will comprise of descriptive statistics (means, standard deviations, correlations, etc.) on the outcome measures and variables listed in **Error! Reference source not found.** below.

The final report will include summary data and descriptive statistics of measurements performed in the study, including all Adverse Events and complications reported during the urodynamic test.

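### Sections 9.5 and 10.1 let a woman with recorded off/on LPP pairs be withdrawn on eligibility grounds, lose those data and be replaced after her response is known; section 11.6 contradicts 10.2 on who counts for safety

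*Combined protocol and SAP*

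**What the plan says.** - **Screening (6.3).** "The first visit includes administering informed consent via telephone script and confirming eligibility". The Table of Events (6.5) marks eligibility once, at this phone visit, and earlier urodynamic results are optional. Full consent, urinalysis and a pregnancy test where applicable come at Visit 2, before the UDT.
- **Exclusion 6 (9.2).** "Active symptomatic uncontrolled bladder instability as determined by the investigator". No urodynamic threshold is attached.
- **Order of the test (7.2, 7.3).** Stimulation is titrated first: "Continue to increase amplitude progressively until discomfort noted". LPP is then assessed with stimulation off and then on, at successive bladder volumes. Under 7.3.8 testing ends at a strong desire to void, or when "bladder reaches major detrusor instability, patient has significant leakage (more than drops), patient has discomfort or any other reason per PI".
- **Late exclusion (9.5).** One of the reasons for which the PI may withdraw a subject is: "If the participant meets an exclusion criterion (either newly developed or not previously recognized) that precludes further study participation".
- **Replacement (9.5).** "Subjects who sign the Informed Consent Form but did not completed the UDT with and without PNS may be replaced".
- **LPP analysis set (10.1).** A subject must have received acute PNS and completed the UDT. Otherwise: "Study subjects that receive acute PNS and do not complete the UDT will be included in safety analysis only".
- **Safety population.** Section 10.2 takes every subject who received acute PNS. Section 11.6 confines safety reporting to eligible subjects who finish the UDT under acute PNS.

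**The concern.** Primary endpoint 2 is the change in LPP with stimulation compared with without. Each woman is her own control and nobody is blinded, so once the first off/on pair is recorded the PI knows roughly how she responded. A rule that still allows her to be removed on eligibility grounds and replaced makes membership of the analysis set depend on a judgement made with the result in view. Exclusion 6 is the clearest example, because the filling trace may be the first objective evidence bearing on it. The women most exposed are those with an urge component, yet the synopsis says the data may support a therapy for mixed as well as stress incontinence.

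Primary endpoint 1 is the identification of study-related adverse events. A safety report confined to women who complete the UDT would leave out those who stopped early, and some of them may have stopped because of harm.

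**Working it through.** The plan offers no figure to reproduce. Section 10 states that there is no hypothesis test and that the sample size of up to 15 is not power-based, and no SD for LPP change is given. The check is therefore a reading of the rules in sequence, followed by an illustration in SD units.

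**Following one subject through the rules**

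1. She passes the phone screen. The Visit 2 urinalysis and pregnancy test bear on exclusions 5 and 9, not on exclusion 6.
2. She receives acute PNS under 7.2, and at least one off/on LPP pair is recorded under 7.3.5 and 7.3.6.
3. Major detrusor instability appears at a later volume. Two routes are open:

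| | Stop under 7.3.8 | Withdrawal under 9.5 |
|---|---|---|
| Label | Listed end of testing | Exclusion recognised late |
| UDT complete? | Most naturally yes | May be judged not complete |
| LPP pairs (10.1) | Analysed | Not analysed |
| Replacement (9.5) | No | Allowed |
| Safety under 10.2 | Counted | Counted |
| Safety under 11.6 | Counted if eligible | Not counted |

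The second column applies only if the PI judges that exclusion 6 is met and precludes further participation, chooses to withdraw her, and her UDT is treated as incomplete. No text prevents that sequence after the pairs have been seen. Section 11.8 would log an unmet criterion as a deviation but does not say what happens to her data.

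**Size of a possible shift in mean LPP change**

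Assumptions, none from the documents: LPP change is normal with SD 1; a proportion p of women show instability, independently of response; every unstable woman with a below-mean response is withdrawn and replaced; 15 are analysed.

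- Chance of removal per woman: p/2.
- Mean among those kept: p × 0.3989 / (1 − p/2), where 0.3989 is the standard normal density at 0.
- Expected number removed: 15 × (p/2) / (1 − p/2).
- Standard error of the mean: 1/√15 = 0.258 SD.

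| p | Removed | Shift (SD) | Shift / SE |
|---|---|---|---|
| 10% | 15 × 0.05/0.95 = 0.8 | 0.0399/0.95 = 0.04 | 0.16 |
| 20% | 15 × 0.10/0.90 = 1.7 | 0.0798/0.90 = 0.09 | 0.34 |
| 30% | 15 × 0.15/0.85 = 2.6 | 0.1197/0.85 = 0.14 | 0.55 |

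If removal is unrelated to response, the shift is 0.

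If women are dropped and not replaced, the cost is precision. The 95% half-width t(0.975, n−1)/√n goes from 0.554 SD at n = 15 to 0.577 at n = 14 and 0.635 at n = 12.

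**Safety.** Suppose one woman of 15 has a related event and stops because of it. Section 10.2 gives 1/15 = 6.7%. Section 11.6 gives 0/14 = 0%.

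**The case against.** Much can be said for the plan, and most of it limits the point.

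- *A reader might infer that eligibility is never settled before stimulation.* The documents do not support that. Section 9.3 ties enrollment to a signed ICF with all criteria met, and the full form is signed at Visit 2 before other activities. Section 9.4 makes a consented woman who fails a criterion a screen failure, and 8.3 restricts enrollment to eligible subjects. What remains is that 9.5 allows eligibility to be reopened after stimulation.
- *A reader might infer that one observation is both an exclusion and a normal stop.* These are different states. Exclusion 6 is a clinical condition that is active, symptomatic and uncontrolled. Section 7.3.8 concerns an event on filling that the plan expects, since Table 1 records volume and detrusor pressure at the first instability. A trace alone need not meet exclusion 6.
- *Loss of data is not automatic.* Withdrawal and replacement are both optional, and a woman with paired LPP who stops under 7.3.8 most naturally counts as complete. That is the sensible reading, but the plan does not make it a rule.
- *A reader might suspect the funder of influencing removals.* Section 6.3 describes its real-time input as concerning test volumes and time points, repeat assessments, troubleshooting and avoiding missed data. Eligibility and withdrawal are not mentioned.
- *Larger biases can be calculated.* Removing the 1, 2 or 3 lowest responders from all subjects shifts the mean by 0.12, 0.21 or 0.28 SD. The instability route reaches only women with instability, so those figures overstate it.
- *The removals would leave a trace.* Withdrawal reasons go on the Study Exit CRF and deviations must be reported, so affected women could be listed. That is correct, but the plan does not ask for a summary that includes their LPP data.
- *Section 11.6 concerns oversight, and 10.2 would probably govern the analysis.* That is likely, but no order of precedence is stated, and 11.6 expressly covers analysis and reporting.

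**Conclusion.** The point holds in a limited form. Sections 9.5 and 10.1, followed as written, permit removal and replacement of a subject on eligibility grounds after her off/on LPP has been seen, and a completed UDT is undefined. Sections 11.6 and 10.2 define different safety populations for primary endpoint 1; that conflict exists however instability is handled.

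The consequence is modest. This is a descriptive early feasibility study with no decision threshold. The range of 0.04 to 0.14 SD assumes deliberate or unconscious selection against below-mean responders and an instability rate of 10% to 30%; the documents support neither assumption, and good-faith removal unrelated to response gives 0. The documents do not show that such removal is intended or likely. The change is worth making because the results may be used to design a powered study and it costs very little.

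**What to change.** 1. **Sections 9.5 and 10.1.** State that once acute PNS has been given, the PI may stop the test for safety at any time, but no subject with at least one recorded off/on LPP pair is removed from the LPP analysis or replaced on eligibility grounds. Her pairs are analysed.
2. **Section 10.1.** Define completion: with at least one pair recorded, a stop for any 7.3.8 reason, including major detrusor instability, counts as a completed UDT. The replacement rule for women without a pair can stay as it is.
3. **Sections 10.1 and 11.8.** Treat an exclusion recognised after stimulation as a protocol deviation, list those subjects, and repeat the LPP summary without them.
4. **Section 11.6.** Reword to cover all subjects who received acute PNS, as in 10.2.

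An eligibility mark at Visit 2 in the Table of Events is optional tidying. It would not resolve this point, because instability on filling appears only after that check.

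The cost is a few sentences, with no new test or visit. The downside is that a few women with genuinely uncontrolled instability may add noise to the main LPP summary; the repeat summary shows how much.
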